The sample size is based on the expected between group difference in the WOOS end scores. The WOOS score 1 year after TSA surgery was 84.6 points in the Danish Shoulder Arthroplasty Registry in 2020 (7). The WOOS score after completing this exercise intervention in a feasibility study was 67 points (15). The assumed common SD was 27.1. The required power was set to 80%. Given a power of 0.80 to detect a difference between the two groups and using a two-sided significance level α =0.05, the estimated sample of each intervention group is 39 patients. Allowing for possible crossovers, loss-to follow-up and drop-outs the total number of patients in each group is 51 (1).

Framework

The overall objective of the trial is to determine whether surgical intervention results in a clinically and statistically significant greater improvement compared to exercise on WOOS, Disabilities of the Arm, Shoulder and Hand (DASH) (16), patient-reported pain intensity at rest, during activity, and nightly pain using the 100 mm VAS, the use of analgesics during the last week (paracetamol, NSAID, opioids) and adverse events. The primary hypothesis is that surgical intervention is superior to the exercise intervention at 12 months.

Blinded interpretation of the results

The blinded interpretation will be of the intention-to-treat analysis. The blinded analysis involves the primary outcome and key secondary outcomes. The principal investigator (JBL) will export data from REDCap and deliver the blinded dataset for analysis to the statistical analysist (AR). The senior statistician (EP) will supervise the analysis. The blinded results from the analysis of treatment A compared with treatment B will be presented to the project group followed by the development of the blinded interpretation. Interpretation version 1 assumes that group A had surgery, while interpretation 2 assumes that group A performed exercise. A draft of the blinded interpretation will be sent for approval by all co-authors. No other outcomes will be analyzed prior to an agreement of the blinded interpretation by all co-authors. All other analyses described in this document will be performed after the blinded interpretation is published (17).

Statistical interim analysis and stopping guidance

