- 7. Other reasons for exclusion include mentally unable to participate or planned absence for more than 14 days in the first 3 months after baseline test
- 8. Unable to communicate in the respective languages of the participating countries.

Recruitment

The CONSORT flowchart will present the number of patients screened, excluded (with reasons), eligible for inclusion, randomized, receiving allocated treatment, withdrawals (with reasons), lost to follow-up (with reasons), included in the ITT analysis, included in the per protocol analysis.

Withdrawal/follow-up

Throughout the trial period the patients are allowed to withdraw from the study at any time. Patients who decide to withdraw will be encouraged to continue in the study as if they have received the intervention. Withdrawal will be classified into two options; (1) complete withdrawal from the study with no further follow-up and data-collection, (2) consent to follow-up assessments and data-collection. The number of withdrawals and the timing of withdrawal will be presented in the CONSORT flowchart (with reasons).

Baseline patient characteristics

Baseline characteristics will be presented as seen in Table 2. Categorical variables will be presented as numbers and percentages. Continuous variables will be presented as mean with

standard deviation (SD), if normally distributed and ad median with interquartile range (IQR) if not normally distributed. No tests of significance will be conducted for the baseline characteristics, imbalances of importance will be noted. Baseline and follow-up values for the primary and secondary outcomes will be presented as part of the analysis, as seen in Table 3.

SECTION 6: ANALYSIS

Outcome definitions

The Western Ontario Osteoarthritis of the Shoulder index score (WOOS)

The primary outcome will be presented as the between group difference on the 12-month follow-up score. WOOS is a valid and reliable patient-reported questionnaire assessing shoulder pain and function in a total raw score ranging from 0-1900, raw scores can be converted to a score from 0-100, where 0 indicates severe problems and 100 indicates no problems.

Key secondary outcomes

Disabilities of the Arm, Shoulder and Hand (DASH) (Lindenhovius et al. 2008); patientreported pain intensity at rest, during activity, and nightly pain using the 100 mm VAS; the use of analgesics during the last week (paracetamol, NSAID, opioids); serious adverse events and adverse events.

Analysis methods

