Descriptive statistics will be presented as means with standard deviation (SD) for all normally distributed continuous variables. Continuous variables that do not follow a normal distribution will be presented as median with interquartile ranges. Normal distribution will be determined by visual inspection of QQ-plots and histograms. Categorical outcomes will be presented as numbers with percentages.

The primary comparison in WOOS between groups will be conducted using a linear mixed model. Intervention group and time (3 months, 12 months) will be included as fixed effects and patient as random. Baseline score, sex, age and study site will also be included as fixed covariates. Interaction between study group and time will be included in the model to estimate treatment effect at each time point. 95% confidence intervals are estimated for each time point.

Due to the repeated mixed model analysis no missing data imputation will be conducted. A sensitivity analysis will be done using an analysis of covariance (ANCOVA) including baseline score, sex, age and study site as covariates with the same ITT approach for time (3 months and 12 months) separately.

Analysis for patient-reported DASH, pain intensity at 3 and 12 months will be analysed similar to the primary comparison. For binary variables (ie. the use of analgesics and adverse events) we use proportions to describe the number of events. For each binary outcome an unadjusted risk difference in proportions with 95% confidence interval of outcomes between study groups. Table 3 illustrates the primary analysis.

Response to treatment for the WOOS change score from baseline to 12 months and 3 months follow-up will be computed for each patient in both treatment groups. Response to treatment will be presented dichotomized (i.e. responder and non-responder) as number and percentage. The patients will be classified as a responder if they reach a minimal important change of 13.3 points or more from baseline to 12 months follow-up (19).

Missing data

As stated above, imputations will not be applied in this study due to the repeated mixed model analysis. Each randomized patient will be included in the intention-to-treat analysis with the collected data. In an attempt to collect data from all randomized patients, patients deciding to withdraw from the study, are still encouraged to attend the follow-up test.

Harms

Adverse and serious adverse events will be presented as number and percentage for each event.

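### The primary mixed model gives baseline WOOS one slope for both visits, so the 12-month difference can be biased if that slope differs by visit and dropout differs by arm

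*SAP*

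**What the plan says.** In SAP Section 6, Outcome definitions, the target is the 12-month contrast: "The primary outcome will be presented as the between group difference on the 12-month follow-up score".

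The primary model is set out under Analysis methods in the same section:

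- Main terms: "Intervention group and time (3 months, 12 months) will be included as fixed effects and patient as random".
- Covariates: "Baseline score, sex, age and study site will also be included as fixed covariates".
- Interaction: "Interaction between study group and time will be included in the model to estimate treatment effect at each time point". No other interaction is named.
- Missing scores: "Due to the repeated mixed model analysis no missing data imputation will be conducted".
- Sensitivity analysis: an ANCOVA with the same covariates, run "with the same ITT approach for time (3 months and 12 months) separately".

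DASH and the pain scales are to be analysed in the same way as WOOS.

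**The concern.** The model lets the treatment effect differ by visit but holds the baseline effect constant. Three months is the end of the exercise block or early recovery after surgery, and 12 months is the end state. The SAP gives no ground for assuming that baseline WOOS predicts both equally well.

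A likelihood analysis without imputation is valid under missing at random only if the mean model is right at each visit. If the true slopes differ, the 12-month scores are adjusted with a slope averaged over the two visits. When the patients still observed at 12 months have a different baseline mix in the two arms, that wrong slope leaves a residue in the treatment difference.

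At stake are the primary estimate and, through the shared model, the DASH and pain estimates.

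**Working it through.** **Plan's own figures first.** The SAP states: "The WOOS score 1 year after TSA surgery was 84.6 points", and "The WOOS score after completing this exercise intervention in a feasibility study was 67 points". The difference is 84.6 − 67 = 17.6, and the common SD is 27.1. By the normal formula, n = 2 × (27.1 × (1.960 + 0.842) / 17.6)² = 37.2, so 38 per group. The exact t calculation gives power 0.798 at 38 and 0.808 at 39, so the stated 39 is reproduced. The step from 39 to 51 implies an allowance of 1 − 39/51 = 23.5%. None of these figures depends on the point below; they supply its scale.

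**Assumed, because the SAP does not give them.** Baseline SD 20; residual correlation 0.5; baseline slopes b3 and b12 between 0.2 and 0.7; logistic 12-month dropout on baseline. Sex, age and site were left out of these simulations.

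**Why two conditions are needed.** Let b be the single fitted slope, r the fitted within-patient correlation, and ΔX the mean baseline among 12-month completers, TSA minus exercise. In large samples:

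bias ≈ [(b12 − b) − r × (b3 − b)] × ΔX

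If b3 = b12 = b, the bracket is zero. If completers have the same baseline mix in both arms, ΔX is zero. Either is enough to remove the bias.

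Worked case: slopes 0.7 and 0.2, 23.5% loss per arm, and loss related to baseline in the exercise arm only (log-odds 1 per SD worse). A large-sample fit gives b ≈ 0.50, r ≈ 0.44 and ΔX ≈ −4.0. Then [(0.20 − 0.50) − 0.44 × (0.70 − 0.50)] × (−4.0) = (−0.388) × (−4.0) = +1.55. Direct simulation gave +1.59.

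**Large-sample bias of the 12-month difference** (true value 17.6; 2 runs of 1,000,000 patients; log-odds 1 per SD):

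| 12-month dropout | Slopes (3 m / 12 m) | SAP model | With baseline-by-time | 12-month ANCOVA |
|---|---|---|---|---|
| None | 0.7 / 0.2 | +0.02 | +0.02 | +0.02 |
| 23.5% per arm, same relation to baseline | 0.7 / 0.2 | −0.05 | −0.03 | −0.03 |
| Baseline-related in exercise only, 23.5% per arm | 0.5 / 0.5 | −0.03 | −0.03 | −0.04 |
| Same | 0.5 / 0.3 | +0.74 | +0.08 | +0.10 |
| Same | 0.7 / 0.2 | +1.59 | +0.03 | +0.03 |
| Same | 0.2 / 0.7 | −1.55 | +0.02 | +0.02 |
| Same relation, 35% exercise and 12% TSA | 0.5 / 0.3 | +0.62 | +0.02 | +0.03 |
| Same | 0.7 / 0.2 | +1.45 | −0.01 | −0.02 |

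Equal slopes gave about 0 under every dropout pattern tried.

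**At 51 per arm, with 8% loss in TSA** (1,500 trials per scenario; shift relative to the model with baseline-by-time):

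- Slopes 0.5 / 0.3, mild dependence on baseline (log-odds 0.5 per SD): +0.3.
- Slopes 0.55 / 0.20: +0.6 with 21% exercise loss and mild dependence; +0.9 with 19% loss and stronger dependence (log-odds 1.0); +1.4 with 29% loss.
- Reversed slopes, 0.20 / 0.55: −1.4.

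Against the SE of 5.6, 1.4 / 5.6 = 0.25; against the effect, 1.4 / 17.6 = 8%.

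**When exercise dropout also depends on the 3-month score** (large sample; 23.5% exercise and 8% TSA loss; log-odds 1 per SD for baseline and for the 3-month residual; range over two runs):

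- Slopes 0.55 / 0.20: SAP model +0.7 to +1.0; ANCOVA −2.3 to −2.5.
- Slopes 0.20 / 0.55: SAP model −1.0 to −1.2; ANCOVA about −2.4.
- With baseline-by-time: within about 0.2 of zero in both.

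**The case against.** The strongest reply is that both conditions are assumed. The SAP gives no baseline SD, no baseline slope by visit and no dropout by arm. The sign of the bias flips with the assumed slopes, so no direction is shown. Patients who cross over are still followed and analysed as randomised, and those who withdraw are encouraged to attend follow-up, so real loss may be below the 23.5% allowance. All of this stands. It limits the point to what can happen and keeps it minor.

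A second reply is that the plan already contains a check, because the 12-month ANCOVA has its own baseline slope. This stands in part. The ANCOVA is unbiased when dropout depends on baseline only. It is off by more than the primary model when dropout also depends on the 3-month score, which is the situation in which a repeated-measures model is most useful.

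A reader might infer that any link between dropout and baseline biases the primary estimate. It does not: with the same dropout in both arms, the misfit cancels in the difference even at slopes of 0.7 and 0.2.

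A reader might also infer that the added term would make the mixed model and the ANCOVA agree on complete data. The planned ANCOVA also lets sex, age and site effects differ by visit. In a complete-data simulation with 102 patients, 7 sites and slopes 0.55 / 0.20, the SD of the difference between the two analyses was 0.86 for the SAP model and 0.40 with the added term. The gap shrinks but remains. The SAP does not say that the ANCOVA is meant to isolate the handling of missing scores.

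**Conclusion.** The point holds in conditional form. As written, the primary model has one baseline slope for two visits. The 12-month contrast can be biased under missing at random when the slopes differ by visit and dropout differs by arm.

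Over the assumed range, the bias is about 0.3 to 1.6 points in either direction, up to about a quarter of a standard error. That is small beside the assumed 17.6-point effect and the SAP's 13.3-point minimal important change. Larger values need extreme patterns. Opposite dropout relations in the two arms gave −1.3 to −3.2 (slopes 0.5 / 0.3 and 0.7 / 0.2). Doubling the log-odds to 2 gave +2.4 for exercise-only dependence and −5.0 for opposite patterns (slopes 0.7 / 0.2). Nothing in the SAP suggests such patterns.

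It would go too far to call the primary analysis invalid or its conclusion at risk. The SAP contains no misstatement or wrong figure here, and the bias alone is unlikely to reverse an effect near 17.6. It would matter more for a smaller or borderline effect. Differential loss is plausible when surgery is compared with exercise, but the SAP documents none.

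**What to change.** Add a baseline-score-by-time interaction to the mixed models for WOOS, DASH and the pain scales, using each outcome's own baseline. Keep group-by-time and report the 12-month contrast from that model. Make the change before unblinding, and preferably before the blinded A-versus-B analysis is run.

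The cost is one line of SAP text and one parameter per model. If the slopes are in fact equal, the SD of the estimate rises by about 1% or less (5.61 to 5.68 in one simulation, 5.59 to 5.62 in another). If they differ strongly, precision can improve (6.06 to 5.83 with slopes 0.7 / 0.2 and the same dropout in both arms). The ANCOVA can stay as planned, read as a partial check.

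### No planned analysis tests 12-month loss that depends on the unseen score, and the primary model cannot include every randomised patient as the SAP states

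*SAP*

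**What the plan says.** All of this is in the SAP, mostly in Section 6.

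- **Primary model** (Analysis methods): WOOS is compared by a mixed model whose structure is set out as follows: "Intervention group and time (3 months, 12 months) will be included as fixed effects and patient as random". The baseline WOOS enters on the covariate side, next to sex, age and site. The group-by-time interaction gives the 12-month effect.
- **Imputation** (Analysis methods): "Due to the repeated mixed model analysis no missing data imputation will be conducted". The Missing data paragraph repeats that "imputations will not be applied in this study due to the repeated mixed model analysis".
- **Sensitivity analysis** (Analysis methods): "A sensitivity analysis will be done using an analysis of covariance (ANCOVA) including baseline score, sex, age and study site as covariates". Each follow-up visit gets its own fit.
- **Who is included** (Missing data): "Each randomized patient will be included in the intention-to-treat analysis with the collected data".
- **Withdrawal** (Section 5, Withdrawal/follow-up): one of the two foreseen types is "complete withdrawal from the study with no further follow-up and data-collection".

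The SAP names no missing-data assumption. The per-protocol and as-treated analyses in Section 4 deal with adherence and crossover, not with missing scores.

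**The concern.** A likelihood-based mixed model without imputation is a sound primary choice, but it is valid only if 12-month scores are missing at random given arm, covariates and the 3-month score. Patients know their treatment, and whether they return may depend on how the shoulder feels at 12 months. A sensitivity analysis for missing data should relax the assumption. The visit-wise ANCOVA tightens it: it uses only patients observed at 12 months and ignores the 3-month score.

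The inclusion sentence also conflicts with the model. Only 3 and 12 months are outcome times, and baseline is on the covariate side. A patient who withdraws completely before 3 months has no outcome row and does not contribute.

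At stake is whether a reader can tell how far the 12-month WOOS result depends on patients who were not seen. DASH and pain follow the primary model, so the gap carries over to them.

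**Working it through.** **Inputs from the SAP.** Section 3, Sample Size: expected WOOS 84.6 and 67, SD 27.1, two-sided alpha 0.05, power 80%, 39 per arm, 51 per arm after allowance. Section 6: responder threshold 13.3 points.

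**1. The plan's own figure.** Difference = 84.6 − 67 = 17.6. The normal approximation is n = 2 × (1.96 + 0.84)² × 27.1² / 17.6², which rounds up to 38 per arm. With the noncentral t, power is 79.8% at 38 and 80.8% at 39, so 39 is reproduced. The sample size is not in question.

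**2. How much could be missing.** (51 − 39)/51 = 12/51 = 23.5%. This allowance covers crossovers, loss to follow-up and drop-out together. Crossovers remain observed under ITT, so 23.5% is a ceiling on planned missingness. Lower rates below are assumed.

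**3. Shift in the estimate.** If a fraction f of one arm is missing and those patients truly score D points worse than the model predicts, the difference moves by f × D. Both values of D are assumed; 13.3 borrows the SAP's threshold as a yardstick.

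| f | D = 13.3 | D = 20 |
|---|---|---|
| 5% | 0.7 | 1.0 |
| 10% | 1.3 | 2.0 |
| 15% | 2.0 | 3.0 |
| 23.5% | 3.1 | 4.7 |

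A departure in the TSA arm means the benefit is overstated; in the exercise arm, understated. Equal departures in both arms cancel.

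**4. Tipping point.** Half-width of the 95% CI = 1.96 × 27.1 × √(2/n observed per arm). The D that brings the lower limit to 0 is (observed difference − half-width)/f.

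- f = 23.5%, n = 39: half-width 12.03. At an observed difference of 17.6: (17.6 − 12.03)/0.235 = 23.7 points. At 13.3 (assumed): (13.3 − 12.03)/0.235 = 5.4 points.
- f = 10%, n = 45.9: half-width 11.09. At 17.6: (17.6 − 11.09)/0.10 = 65.1 points. At 13.3: (13.3 − 11.09)/0.10 = 22.1 points.

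These use the unadjusted SD and hold the half-width fixed as D changes. Covariate adjustment would narrow the interval, so they are guides only.

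**5. Can the ANCOVA reveal the problem?** A simulation was run with 400 replicates per mechanism, 51 per arm, a true difference of 17.6, SD 27.1 and about 23.5% missing at 12 months. Assumed correlations were 0.6 between follow-up visits and 0.4 with baseline. Both models adjusted for baseline only. The simulation standard error is about 0.3.

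| Loss at 12 months | Mixed model | ANCOVA |
|---|---|---|
| Completely at random | 17.7 | 17.7 |
| TSA arm: depends on 3-month score | 17.7 | 20.5 |
| TSA arm: depends on unseen 12-month score | 22.4 | 23.3 |

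In the second row the ANCOVA is the biased analysis, and the gap of 2.8 points signals a problem. In the third, the mixed model is off by 22.4 − 17.6 = 4.8 and the ANCOVA by 23.3 − 17.6 = 5.7. They differ by only 0.9, so close agreement would falsely reassure.

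**6. Who enters the model.** If half of those lost at 12 months also lack a 3-month score (assumed), about 90 of 102 patients enter the mixed model and about 78 of 102 the 12-month ANCOVA.

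**The case against.** The SAP never says that the ANCOVA tests a missing-data assumption. It is a fair check on model form: a single random patient effect and covariate effects shared across visits. That stands, and it is a reason to keep the ANCOVA. It leaves nothing else in the missing-data role.

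The inclusion sentence ends with a qualifier about collected data and can be read as saying that nobody is excluded for non-adherence. That is probably its intent, but a baseline score alone still cannot enter this model.

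Some stronger readings are tempting but not supported:

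- *That comparing the two analyses says nothing about informative dropout.* Loss driven by the 3-month score does separate them. Only loss driven by unseen 12-month scores escapes.
- *That the plan expects 23.5% missing.* That figure includes an unstated share of crossovers, whose scores are observed.
- *That the CONSORT count will be wrong.* Section 5 asks for withdrawals, losses and the number in the ITT analysis as separate entries, and does not fix the last at all randomised.
- *That the primary conclusion is fragile.* At the planned difference it is fairly robust, and a one-arm grid of 0 to 20 points would not reach the tipping point of about 24. Fragility arises only if the observed difference is clearly smaller.

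**Conclusion.** The point holds in two limited parts. First, nothing planned examines 12-month loss that depends on the unobserved score, and the one sensitivity analysis rests on a stronger assumption than the model it accompanies. Second, the statement that every randomised patient is in the ITT analysis is untrue for anyone without a post-baseline WOOS, a case the SAP itself foresees.

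The size is moderate and conditional. A one-arm departure of 13.3 points moves the difference by 1.3 to 3.1 points across 10% to 23.5% missing, which is 8% to 18% of 17.6. Whether that matters depends on the observed difference and the actual loss, neither of which is known. The simulation rests on assumed correlations and loss mechanisms and shows direction, not expected bias. This is an inexpensive improvement to an otherwise reasonable primary analysis, not a fault that invalidates it.

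**What to change.** 1. Keep the mixed model as primary and the ANCOVA as supportive.
2. State that the mixed model assumes missing at random given arm, covariates and the 3-month score.
3. Add one delta-adjusted (tipping-point) multiple-imputation analysis, or an equivalent pattern-mixture analysis, of 12-month WOOS on all randomised patients. Vary the shift separately by arm, and extend the range until the conclusion changes or the shift becomes implausible. Amend the blanket statement against imputation to allow this.
4. Make it available with the blinded ITT results. Section 3 bases the blinded interpretation on the ITT analysis and defers the other analyses until after that is published, so a later result would come after the wording is settled.
5. Reword the inclusion sentence to patients with at least one post-baseline WOOS, or model baseline as an outcome with a mean common to both arms so that everyone with a baseline score contributes. Either way, report by arm the number with no post-baseline WOOS.

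The cost is a few lines of SAP text and a short extra analysis in R on data already being collected. The downside is one more result to report.

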In hip and knee OA exercise is recommended as the first-line treatment (4). The effectiveness of exercise and the effectiveness of TSA in patients with glenohumeral OA is unknown, as no randomized trials have directly compared TSA to a non-surgical treatment (5). In order to provide a trustworthy and evidence-based foundation for clinical decisions it is important to conduct a randomized controlled trial where surgical treatment is compared to non-surgical treatment in patients with glenohumeral OA.

The primary aim of this trial is to examine if surgical treatment followed by standard care is superior to a 12-week exercise programme in patients with primary glenohumeral OA. The primary outcome is the Western Ontario Osteoarthritis of the Shoulder index score (WOOS), measured 12 months after initiating the treatment. The primary hypothesis is that surgical intervention is superior to the exercise intervention at 12 months (1).

The key secondary objectives are (1):

- To investigate the effectiveness of total anatomical shoulder arthroplasty followed by standard rehabilitation compared to a 12-week physiotherapist-supervised exercise programme, on (1) pain intensity, (2) activities of daily living, (3) use of analgesics and (4) shoulder-related quality of life in patients with glenohumeral OA.
- 2. To investigate the safety of total anatomical shoulder arthroplasty followed by standard rehabilitation compared to a 12-week physiotherapist-supervised exercise programme on occurrence of adverse events from baseline to 12 months after initiating the treatment, in patients with glenohumeral OA.

Exploratory objectives:

- 1. To investigate the external validity of the randomised controlled trial on total anatomical shoulder arthroplasty and physiotherapist-supervised exercise in patients glenohumeral OA by comparing patient characteristics and patient-reported WOOS scores from baseline to 12 months after initiating the treatment, in patients included in the randomised controlled trial versus those declining to participate but included in the follow-up cohort.
- 2. To investigate objectively measured physical upper extremity activity level from baseline to 12 months using tri-axial (Axivity, UK) accelerometers, in patients with glenohumeral OA eligible for total anatomical shoulder arthroplasty.

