- 3. To assess the cost-utility of total anatomical shoulder arthroplasty followed by standard care compared to a 12-week physiotherapist-supervised progressive exercise programme on quality-adjusted life years (QALYs) gained from baseline to 12 months after initiating the treatment, in patients with glenohumeral OA.

SECTION 3: STUDY METHODS

Trial Design

The PROACT trial is a multicenter randomized controlled and investigator blinded trial, the reporting of the trial will follow the "*Consolidated Standards of Reporting Trials*" (CONSORT) statement (12). Patients are recruited from the orthopaedic departments at Aarhus University Hospital, Aalborg University Hospital, Viborg Regional Hospital and Silkeborg Regional Hospital in Denmark, at Tampere University Hospital, Central Finland Hospital in Finland and Oslo University Hospital in Norway.

The Statistical Analysis Plan (SAP) is reported in accordance with the "Guidelines for the Content of Statistical Analysis Plan in Clinical Trials" (13).

The PROACT trial is registered at www.clincaltrials.gov with the number NCT04845074. The Central Denmark Region Committee on Biomedical Research Ethics (Journal No 1-10-72-29-21) and the Danish Data Protection Agency (Journal No 1-16-02-199-21), The Regional Ethics Committee of the Expert Responsibility area of Tampere University Hospital (ref ETL R21089) and The Regional Committee for Medical and Health Research Ethics Region South-East Norway (Ref. 269784) have approved the trial.

Randomisation

The included patients will be randomised with a 1:1 allocation to TSA or exercise after their baseline assessment. The randomisation is stratified by recruitment site with randomly selected block sizes and done by a computer-generated list of random numbers using the randomization tool in Research Electronic Data Capture (REDCap), developed by an independent data manager (14). During the trial period administrators of the randomisation procedure are blinded to block sizes and randomisation sequence at all times.

Sample Size

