There has not been planned any formal statistical interim analysis for the PROACT trial. The final deadline for patient recruitment was a priori set to April 2024 but has since been moved to November 2024 due to delays in recruitment.

Timing of final analysis

The final analysis for the primary outcome, the end scores on WOOS at 12 months, will be performed after the last follow-up assessment at 12-months. The main publication of the trial will be prepared when these data are available.

In addition, papers on 2-, 5-, and 10-years follow-up will be performed, when these follow-up assessments are available.

Timing of outcome assessments

The trial consists of six time points; baseline, 12-weeks, 12-months, 2 years, 5 years and 10 years. An overview of the assessments and procedures has been presented in the protocol (Table 1).

SECTION 4: STATISTICAL PRINCIPLES

Confidence intervals and P values

For the primary outcome the statistical tests will be two-sided and a p-value <0.05 will be considered statistically significant. Confidence intervals will be 95% (95% CI) and two-sided. For the secondary outcomes the use of p values will be interpreted with care (18).

Adherence and protocol deviations

Adherence is defined as the ability to follow the allocated treatment. For the exercise group adherence is related to the number of attended supervised exercise sessions, good adherence has been predefined as participation in at least 70% of the supervised exercise sessions, during the first 12-weeks. Table 7 illustrates this.

There are predefined protocol deviations regarding adherence:

- 1. Patients randomized to exercise undergoing TSA in the follow-up period
- 2. Patients randomized to TSA not undergoing TSA in the follow-up period

Analysis populations

The primary analysis will be based on the Intention to Treat (ITT) principle. Patients allocated to a treatment group (TSA or exercise) should be followed up, assessed and analysed as members of that group, regardless of their adherence to the planned course of treatment.

Response to treatment will be described for both treatment groups, regardless of their adherence to the planned course of treatment.

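### Analgesic use, a key secondary outcome, gets an unadjusted risk difference although its baseline value is collected; some precision is lost, and Tables 3 and 4 head the same row Adjusted

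*SAP*

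**What the plan says.** Section 6, Analysis methods, treats analgesic use and adverse events as binary and plans for them: "For each binary outcome an unadjusted risk difference in proportions with 95% confidence interval of outcomes between study groups". The next sentence reads "Table 3 illustrates the primary analysis".

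For the WOOS model the same section states "Baseline score, sex, age and study site will also be included as fixed covariates", and DASH and pain are to be handled in a similar way.

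Analgesic use has standing in the plan. The key secondary objectives include "3) use of analgesics and (4) shoulder-related quality of life in patients with glenohumeral OA", and Section 6 lists it among the key secondary outcomes. Under Blinded interpretation of the results: "The blinded analysis involves the primary outcome and key secondary outcomes".

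Table 1 marks analgesic consumption at baseline, 3 months and 12 months. Tables 3 and 5 have baseline columns for it in each arm, and Table 5 counts it as yes or no. In Section 3, Randomisation: "The randomisation is stratified by recruitment site with randomly selected block sizes".

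Tables 3 and 4 each have one between-group result column, headed *Adjusted*, and the analgesic and adverse-event rows lie under it. The Table 3 footnote says that these two rows use a risk difference, but not whether it is adjusted.

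**The concern.** Two things look wrong.

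First, a baseline measurement of the outcome is in hand and goes unused. The SAP gives no reason to treat analgesic use differently from WOOS, DASH and pain. Adverse events have no baseline value, so the unadjusted choice is natural there; that does not carry over to analgesic use. Section 4 adds "For the secondary outcomes the use of p values will be interpreted with care", so readers will rely on the estimate and its interval, and the width of that interval is what is at stake.

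Second, the text says unadjusted and the table shells say adjusted. No covariates are named for an adjusted binary analysis. Two analysts could follow the document in good faith and fill the same cell with different numbers.

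A smaller point goes with these. The SAP explains the absence of imputation by the repeated-measures mixed model, but no such model is fitted to analgesic use.

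**Working it through.** **The plan's own figure.** The SAP gives no precision or power figure for analgesic use. Its only design figure is for WOOS: difference 84.6 − 67 = 17.6, SD 27.1, two-sided 5%, power 80%. The normal formula gives 2 × (1.96 + 0.84)² × (27.1/17.6)² ≈ 37.2, so 38 per group. The t-test version gives 38.2, so 39, as stated. Then "Allowing for possible crossovers, loss-to follow-up and drop-outs the total number of patients in each group is 51", which implies an allowance of 12/51 = 23.5%. Both 51 and 39 per arm are used below.

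**Assumptions, not from the SAP.** Analgesic use is 70% at baseline, and 60% versus 40% at 12 months. φ is the within-arm correlation between baseline and 12-month use.

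**Precision.** The unadjusted half-width is 1.96 × √(0.6×0.4/n + 0.4×0.6/n) = 1.96 × √(0.48/n). Adjusting for baseline use multiplies it by √(1 − φ²). The equivalent number of extra patients is 102/(1 − φ²) − 102.

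| φ | Half-width, 51 per arm (points) | Half-width, 39 per arm (points) | Equivalent extra patients (of 102) |
|---|---|---|---|
| 0 (same as unadjusted) | 19.0 | 21.7 | 0 |
| 0.2 | 18.6 | 21.3 | 4 |
| 0.3 | 18.1 | 20.7 | 10 |
| 0.4 | 17.4 | 19.9 | 19 |

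**How large φ can be.** For two yes/no variables with proportions a and b, the maximum is φ = [min(a,b) − ab] / √[a(1−a)b(1−b)]. With a = 0.70:

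- b = 0.40: (0.40 − 0.28)/√(0.21×0.24) = 0.53
- b = 0.30: (0.30 − 0.21)/√(0.21×0.21) = 0.43
- b = 0.20: (0.20 − 0.14)/√(0.21×0.16) = 0.33

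In the arm with 40% use, φ = 0.5 would need joint use of 0.28 + 0.5 × 0.2245 = 0.392. Then 98% of 12-month users would have been baseline users, and under 3% of baseline non-users would have started.

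**Chance imbalance is the same loss, not an additional one.** The regression slope is φ√(0.24/0.21). The SD of the between-arm difference in baseline use is √(2×0.21/51) = 9.1 points. The square of their product, divided by the unadjusted variance 0.48/51, equals φ²: 4%, 9% and 16% at 0.2, 0.3 and 0.4.

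**Simulation check.** This used 2,500 trials per setting with 102 patients, site-stratified blocks, seven sites with assumed shares, and small sites pooled. Change in variance against the unadjusted estimate, with no site differences:

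| Model | φ = 0 | φ = 0.2 | φ = 0.3 | φ = 0.4 |
|---|---|---|---|---|
| Baseline use | +0.8% | −2.3% | −9.6% | −17.1% |
| Site | +0.5% | +0.5% | +0.6% | +0.2% |
| Both | +1.5% | −1.7% | −8.7% | −16.4% |

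With sites differing by an SD of 10 points, the model with both gives +0.4%, −2.6%, −8.8% and −14.0%. Coverage of the unadjusted and the baseline-plus-site intervals was 0.937–0.951. A separate simulation with linear adjustment found both estimates unbiased, with a standard-error ratio of 1.00–1.01 at φ of 0 to 0.1 and about 0.96 at 0.3.

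**The case against.** The strongest reply is that the plan makes no error of inference. It fixes in advance a simple, model-free risk difference, a defensible choice for about 100 patients at seven sites. At a correlation of 0.2 to 0.3 the interval narrows by less than one point on 19, which would rarely change a conclusion. The column heading suits the five continuous rows, the binary rows carry an asterisk and a footnote, and relabelling alone would remove the clash.

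Much of this stands. The gain is small at low correlation, and site contributes nothing measurable to precision. But relabelling leaves a collected predictor of a key secondary outcome unused. The footnote does not settle the conflict, because a risk difference can be adjusted or unadjusted.

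A reader might infer that the unadjusted estimate is biased, or that a chance baseline imbalance makes it so. The documents do not support that for the intention-to-treat comparison: randomisation makes it unbiased, and imbalance is part of its sampling variance. The per-protocol half of Table 3 and the as-treated Table 4 are not protected by randomisation, so there it matters more that readers know which estimate they see.

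A reader might also infer that missing 12-month values call for multiple imputation. On assumed rates, the shift is at most 0.4 points if missingness is alike in both arms. If missingness depends on 3-month use in one arm only, it is 0.6–1.7 points at 12% missing. At 23.5% missing it is 1.4–3.8, an upper limit because the allowance also covers crossovers. These are small shifts from constructed scenarios. They justify correcting the sentence, not adding an analysis.

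**Conclusion.** The point holds as one of efficiency and consistency. The disagreement between Section 6 and Tables 3 and 4 is certain from the text. The loss of precision is real if baseline use predicts later use, and modest: on the assumed rates and 51 per arm, 0.4 to 1.6 points of a 19.0-point half-width at correlations of 0.2 to 0.4. The SAP supplies neither the rates nor the correlation, so this is a range under assumptions and not an estimate for this trial.

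A reader might expect larger gains by taking a correlation of 0.5 or more. That is close to the attainable maximum of 0.53 in the base case and impossible in an arm with 30% or 20% later use, where the maxima are 0.43 and 0.33. Nothing in the SAP supports such a figure. The primary outcome is not affected.

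**What to change.** Settle this before the blinded results are produced, so that the choice cannot look data-driven.

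- **Section 6, analgesic use (yes/no) only.** Make the main estimate at 3 and at 12 months a standardised (g-computation) risk difference with 95% confidence interval, from a logistic model with group, baseline use and site. Site is included because it is the stratification factor, not for precision. Pool small sites by a rule fixed before unblinding. Keep the unadjusted difference as supportive.
- **Tables 3 and 4.** Label each binary row adjusted or unadjusted. Adverse events stay unadjusted.
- **Missing data.** State that the mixed-model reason for not imputing does not cover analgesic use, since no mixed model is fitted to it. No multiple imputation is needed.

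The cost is SAP wording, table labels and a little more R code, with no new data. The downsides are possible pooling of sites and a 1–2% loss of variance efficiency if baseline use turns out not to predict later use.
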